2.4. Methods

Retrospective, multi-center study

CV events are optimally registered by hospital medical records or can be obtained with telephonic interview using a structured questionnaire aimed to recognize the presence of the above-mentioned comorbidities and the occurrence of CV events.

Statistical analysis:

CV event rates will be expressed as the number of events per 1000 person-years.

Kaplan-Meier analysis will be used to construct survival curves and compute risks. Cox regression will be used for time-to-event analysis, and hazard ratios (HRs) computed with accompanying 95% confidence intervals (95% CI). Analysis will be stratified according to post-dexamethasone cortisol levels with three pre-specified cutoffs: ≤ 50 nmol/L (1.8 μ g/dL), 51-138 nmol/L (1.9-5.0 μ g/dL) and > 138 nmol/L (> 5 μ g/dL). However, additional cutoffs might be analysed as well.

Depending on the level of comprehensive documentation of the patients' characteristics two cohorts will be separately analysed:

- Cohort A: all requested data are available
- Cohort B: patients with missing data, but the following data are available: date of diagnosis the adrenal incidentaloma, result of 1mg DST, and survival status (or date of death).

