2.5. Requested clinical annotations (type, justification)

Inclusion criteria:

- Age ≥ 18 years
- Adrenal mass detected by sensitive imaging tests (CT or MRI) not done for suspected adrenal disease since 1-1-2000 (modified in Oct 2018 to 1-1-1996 to allow longer follow-up time)
- Imaging characteristics typical of adrenal adenoma: unenhanced or delayed enhanced CT, MRI with chemical shift and FDG-PET are all acceptable to secure this diagnosis.

- In the absence of appropriate imaging study, results of 12-month follow-up showing unchanged mass characteristics can be considered as surrogate criterion.
- Availability of 1-mg overnight dexamethasone test results done at diagnosis or during follow-up
- Follow-up duration of at least 36 months (from the date of diagnosing the adrenal mass the first time)
- Availability of follow-up data on living status and occurrence of CV events (telephone interview allowed to capture data)

Exclusion criteria:

- Presence of clinical features of overt Cushing's syndrome
- UFC $\geq 2 \times$ ULN
- ACTH-dependent Cushing syndrome
- Any active malignancy

Minimum clinical annotations:

- Date of birth, date of diagnosis
- Imaging characteristics (mass size, density on unenhanced CT (HU units), absolute or relative wash-out on delayed enhanced CT, results of MRI with chemical shift, results of FDG-PET, or imaging during follow-up > 12 months after initial imaging demonstrating unchanged tumor size)
- Serum cortisol following 1-mg DST, UFC, plasma ACTH (only serum cortisol after dexamethasone will be entered into the statistical model)
- Presence of obesity, hypertension, diabetes, dyslipidemia at initial diagnosis
- Information on prevalent CV events
- Date of last follow-up (date of death)
- Presence of obesity, hypertension, diabetes, dyslipidemia at last follow-up
- Information on incident CV events and date of first event

Minimum expected patient cohort per center: 50

Data acquisition via ENS@T registry

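### Cohort A is defined by completeness on every requested item, including hormone tests that no model uses and comorbidity status at last follow-up, so membership may depend on work-up and on survival

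*Combined protocol and SAP*

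**What the plan says.** Section 2.4 sorts patients by how complete their records are and analyses the two groups on their own. Membership of the first group is settled by one line: "Cohort A: all requested data are available". Everyone else goes to Cohort B, provided three facts are known: when the mass was diagnosed, what the dexamethasone test showed, and whether the patient is alive (or when death occurred). No cohort is named as primary for any endpoint, and no pooling rule or missing-data method is given.

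The only list of requested data is in section 2.5. Three of its lines matter here. The hormone line reads "Serum cortisol following 1-mg DST, UFC, plasma ACTH (only serum cortisol after dexamethasone will be entered into the statistical model", so UFC and ACTH are asked for but stay out of the model. A separate line asks for the four comorbidities a second time, after baseline: "Presence of obesity, hypertension, diabetes, dyslipidemia at last follow-up". The list also asks for CV events arising during follow-up and when the first one happened.

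Other text bears on the point. Section 2.3 starts the overall survival (OS) clock at discovery of the mass and includes comorbidity rates in the aim. The inclusion criteria in 2.5 require follow-up information on vital status and cardiovascular (CV) events for every patient. The exclusion criteria include a UFC threshold. Sections 2.3 and 2.4 allow a telephone questionnaire to fill gaps.

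**The concern.** An analysis set should be decided by what its analysis needs, as far as possible with information fixed at time zero. The Cohort A rule departs from this in two ways.

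First, a patient with full dates, a dexamethasone result, baseline comorbidities and CV events leaves Cohort A if ACTH was never measured, although ACTH plays no part in the model. In a retrospective study, whether ACTH or UFC exists depends on what was ordered in routine care.

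Second, comorbidity status at last follow-up is recorded after time zero. For a patient who dies, last follow-up is the date of death. If that status is harder to establish for those patients, entry to Cohort A depends partly on the primary outcome.

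At stake are the precision of Cohort A estimates, the event rates per 1000 person-years and Kaplan-Meier risks that section 2.4 promises and, under a further condition, the hazard ratios (HRs) between cortisol bands.

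**Working it through.** The documents give no sample size, event count or completeness rate, so there is no figure to reproduce. Every numerical input below is an assumption.

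**1. Reading the rule against the list.** Taken literally, the Cohort A rule requires UFC, ACTH and last-follow-up comorbidity, because all three are in the only list of requested data. The imaging line ends with an alternative, "or imaging during follow-up > 12 months after initial imaging demonstrating unchanged tumor size", so it need not demand every imaging test; the point does not rest on imaging. Long lists thin a complete-data cohort quickly: with independent items each 90% complete, 0.9^4 = 66% of patients qualify on 4 items and 0.9^12 = 28% on 12.

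**2. Precision within Cohort A.** Assume 2000 patients split 55/35/10% over the bands ≤ 50, 51-138 and > 138 nmol/L, with events in 15/20/25%. Events are 2000 × 0.55 × 0.15 = 165, 2000 × 0.35 × 0.20 = 140 and 2000 × 0.10 × 0.25 = 50. Use SE(log HR) ≈ √(1/d1 + 1/d0), and multiply each d by the share of that band with all items.

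| Share complete (≤ 50 / 51-138 / > 138) | SE ratio, 51-138 vs ≤ 50 | SE ratio, > 138 vs ≤ 50 |
|---|---|---|
| 0.50 / 0.85 / 0.95 | 1.247 | 1.128 |
| 0.30 / 0.70 / 0.90 | 1.518 | 1.276 |
| 0.70 / 0.80 / 0.90 | 1.154 | 1.089 |

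First row, first ratio: √(1/119 + 1/82.5) ÷ √(1/140 + 1/165) = 0.1433 ÷ 0.1149 = 1.247. The ratios compare Cohort A alone with all patients. They are the full loss only if Cohort B adds nothing to inference.

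**3. Absolute mortality.** Assume 15% die, with completeness 80% in survivors and 60% in the dead.

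- Cohort A: 0.15 × 0.60 / (0.15 × 0.60 + 0.85 × 0.80) = 0.09 / 0.77 = 11.7%.
- Cohort B: 0.15 × 0.40 / (0.15 × 0.40 + 0.85 × 0.20) = 0.06 / 0.23 = 26.1%.

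Neither recovers 15%.

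**4. Contrast between bands.** Keep 15% deaths and 80% survivor completeness in both bands, but let completeness among the dead be 70% in > 138 and 55% in ≤ 50. The odds ratio is multiplied by 0.70 / 0.55 = 1.27. The risks become 0.105 / 0.785 = 13.4% and 0.0825 / 0.7625 = 10.8%, a risk ratio of about 1.24 where the truth is 1.

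**5. Effect on the Cox HR.** This was simulated with 120,000 patients, 40% in a higher-cortisol group, a baseline death rate of 15 per 1000 person-years, a true HR of 1.5 and follow-up of 3 to 15 years.

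| Completeness: low cortisol alive, dead; high cortisol alive, dead | Deaths per 1000 person-years, low vs high | HR |
|---|---|---|
| Everyone kept | 15.0 vs 23.1 | 1.54 |
| 50%, 50%; 80%, 80% (work-up only) | 15.0 vs 23.1 | 1.54 |
| 80%, 50%; 80%, 50% (death only) | 9.6 vs 15.1 | 1.58 |
| 50%, 25%; 80%, 70% (more loss of low-cortisol deaths) | 7.9 vs 20.6 | 2.61 |
| 50%, 45%; 80%, 40% (more loss of high-cortisol deaths) | 13.6 vs 12.3 | 0.90 |

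Selection on work-up alone leaves rates and HR intact. Selection on death distorts the rates and barely moves the HR. Serious HR bias appears when the loss among the dead differs by band, and it can go either way.

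**The case against.** The strongest defence is that nobody is discarded. Patients with gaps go to Cohort B, which is also analysed. This stands in part: OS keeps these patients, and the standard-error ratios describe Cohort A alone. But separate analysis without a primary cohort or a pooled estimate still splits the primary endpoint by documentation.

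A reader might infer that event-free survival (ES) and CV mortality rest on Cohort A because Cohort B's minimum set lists no CV data. The documents do not support that. The inclusion criteria require CV follow-up for everyone, so Cohort B patients should be able to contribute.

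A reader might also infer that missing UFC or ACTH biases the HR, or falls mainly on the ≤ 50 nmol/L band. More testing after an abnormal dexamethasone result is plausible, but the documents give no data on it, and selection of that kind alone left the simulated HR unchanged.

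UFC is not irrelevant to the study: it serves an exclusion criterion, and ACTH may inform another. That is a reason to collect them. It does not make a result necessary for analysis, since having one is not an inclusion criterion and Cohort B admits patients without it. Likewise, last-follow-up comorbidity is needed for the comorbidity aim, but not for OS or CV endpoints.

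Telephone interview can recover some comorbidity data, but not a test that was never done. The questionnaire is meant to capture deaths too, yet the plan does not say who would then be interviewed or whether comorbidity would be asked about.

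**Conclusion.** The point holds as a defect in how the analysis set is defined. Membership of Cohort A turns on two tests outside the model and on a post-baseline item.

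The sure consequence, wherever UFC or ACTH is missing in an otherwise usable patient, is lost precision in Cohort A: 9% to 52% on the standard error across the assumed patterns, less if Cohort B is also used. The possible consequence is selection on survival, which would make rates and Kaplan-Meier risks too low in A and too high in B if the dead are less complete.

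It would go too far to say that Cohort A mortality is understated or that the HR is inflated. Both depend on completeness rates that the plan does not give, and the HR could move in either direction. The figures of 11.7%, 26.1%, 1.27 (odds) and 1.24 (risk) show what modest differences in completeness would do; they do not estimate what happened.

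**What to change.** In section 2.4, define the main analysis sets by endpoint, among eligible patients:

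- **OS set:** date of discovery, post-dexamethasone cortisol and dated vital status.
- **ES and CV mortality set:** the same, plus prevalent and incident CV event information, which the inclusion criteria already call for on the follow-up side.
- **Comorbidity set:** the only one that requires comorbidity at last follow-up.

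State that availability of UFC, ACTH or last-follow-up comorbidity does not decide entry to the first two sets. Where adjusted models are fitted, impute missing baseline covariates; do not make them an entry condition. The plan names no adjustment covariates, so these would have to be listed. Keep the present all-data Cohort A as a sensitivity analysis. It also addresses patients whose UFC-based exclusion could not be checked. Report completeness by cortisol band and vital status, so that the selection can be judged.

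The cost is a few lines in 2.4 and a re-run of the data cut, with no new data collection. The downside is that the main sets will include some patients without UFC or ACTH. The ES set still relies on post-baseline CV information, which that endpoint cannot avoid.

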2.5. Requested clinical annotations (type, justification)

Inclusion criteria:

- Age ≥ 18 years
- Adrenal mass detected by sensitive imaging tests (CT or MRI) not done for suspected adrenal disease since 1-1-2000 (modified in Oct 2018 to 1-1-1996 to allow longer follow-up time)
- Imaging characteristics typical of adrenal adenoma: unenhanced or delayed enhanced CT, MRI with chemical shift and FDG-PET are all acceptable to secure this diagnosis.

- In the absence of appropriate imaging study, results of 12-month follow-up showing unchanged mass characteristics can be considered as surrogate criterion.
- Availability of 1-mg overnight dexamethasone test results done at diagnosis or during follow-up
- Follow-up duration of at least 36 months (from the date of diagnosing the adrenal mass the first time)
- Availability of follow-up data on living status and occurrence of CV events (telephone interview allowed to capture data)

Exclusion criteria:

- Presence of clinical features of overt Cushing's syndrome
- UFC $\geq 2 \times$ ULN
- ACTH-dependent Cushing syndrome
- Any active malignancy

Minimum clinical annotations:

- Date of birth, date of diagnosis
- Imaging characteristics (mass size, density on unenhanced CT (HU units), absolute or relative wash-out on delayed enhanced CT, results of MRI with chemical shift, results of FDG-PET, or imaging during follow-up > 12 months after initial imaging demonstrating unchanged tumor size)
- Serum cortisol following 1-mg DST, UFC, plasma ACTH (only serum cortisol after dexamethasone will be entered into the statistical model)
- Presence of obesity, hypertension, diabetes, dyslipidemia at initial diagnosis
- Information on prevalent CV events
- Date of last follow-up (date of death)
- Presence of obesity, hypertension, diabetes, dyslipidemia at last follow-up
- Information on incident CV events and date of first event

Minimum expected patient cohort per center: 50

Data acquisition via ENS@T registry

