2.3. Aim

The primary aim of the study is to assess mortality, CV events and the rate of vascular and metabolic comorbidities potentially linked to cortisol excess (hypertension, diabetes, dyslipidemia, obesity) in patients with adrenal incidentalomas and calculate HRs for patient groups stratified by cortisol values following the 1-mg overnight dexamethasone test.

Two types of CV events are differentiated:

- ‘major CV events’: clinically symptomatic myocardial infarction or stroke followed by hospitalization, or CV-related death.
- ‘minor CV events’: any other type of myocardial infarction and therapeutic procedures for coronary heart disease (PTCA, surgical bypass), any stroke, transient ischemic attack, heart failure, deep vein thrombosis, pulmonary embolism.

CV events are optimally registered by hospital medical records reporting one (or more) of the followings: acute myocardial infarction and related therapeutic procedures (PTCA, surgical bypass), stroke, TIA, heart failure, deep vein thrombosis, pulmonary embolism, sudden death, or death from cardiovascular cause.

However, it will be allowed to obtain data with telephonic interview using a structured questionnaire aimed to recognize the presence of the above-mentioned comorbidities and the occurrence of major CV events (clinically symptomatic myocardial infarction, stroke, death).

We will assess:

- Overall Survival (OS) as primary endpoint, defined as the time interval between the date of discovery of adrenal incidentaloma and the date of death from any cause, in patients stratified by different cortisol cut-offs.
- Event-free Survival (ES), defined as the time interval between the date of discovery of adrenal incidentaloma and the date of occurrence of a 'major' and/or 'minor' CV event, in patients stratified by different cortisol cut-offs.
- CV mortality, defined as death from any CV cause, in patients stratified by different cortisol cut-offs. Other causes of death will be specified, as well.

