2.8. Projected time frame
Deadline for affirmation of participation in the study (e-mail to [contact]): 31-10-2018
Deadline for data acquisition: 31-11-2018
Deadline for data analysis: 31-03-2019
Expected manuscript submission: 31-12-2019
Targeted Journals: depending on outcome

3. Publication policy

1. Recipient scientist formally agrees with the provider(s) - at the time of the request or soon after the provider(s) have accepted the collaboration - the(ir) presence (if any) as co-authors in the publications originating from the collaboration.
2. Number of authors per center and order of authorships are specified as a general rule as follows: 51-100: 1 author; 101-150: 2; 151-200: 3; 201-250: 4; 251-350: 5; 351-450: 6; 450-600: 7. A minimum of 50 patients per center to qualify for authorship.
3. The order of authors depends on the number of recruited patients per center. However, due to the work already done and their role in analysing the data, the following authorship positions are already predefined: [name] as first author, [name] as last author. The next 5 most attractive positions will be given to the 5 best recruiting centers and these centers can choose in downward order on the respective position.
4. Depending on the contribution of each centre, or if number of authors has to be limited on the basis of a specific journal style, co-authors will be represented as “on behalf of ENS@T” and placed in an appropriate list depending on the Journal format (acknowledgment or collaborators list). In this case the recipient scientist will contact all provider(s) and obtain agreement.
5. The authors agree to acknowledge ENS@T contribution: “This project has been supported by the European Network for the Study of Adrenal Tumors (ENS@T).”

4. Conditions of data usage

1. The Recipient scientist will use the data for research purposes only.
2. The data will be used by the Recipient scientist solely in connection with the Research Project as outlined above.
3. The Recipient scientist shall use the data in compliance with all applicable laws and government regulations of the Recipient's country.
4. The Recipient Scientist shall not release the data to any person other than the personnel under the Recipient Scientist's direct supervision.
5. When the Research Project is completed, a detailed description of the use of the data will be made available to the appropriate ENS@T Working Group

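### The entry window was moved back from 2000 to 1996 in October 2018, but the Kaplan-Meier and Cox comparisons of cortisol bands make no use of period of diagnosis

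*Combined protocol and SAP*

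**What the plan says.** Section 2.5 sets the start of the imaging window as "since 1-1-2000 (modified in Oct 2018 to 1-1-1996 to allow longer follow-up time" and requires "Follow-up duration of at least 36 months (from the date of diagnosing the adrenal mass the first time". Section 2.8 gives 31-10-2018 as the last day for centres to confirm participation, then "Deadline for data acquisition: 31-11-2018" (not a calendar date; read here as 30 November 2018) and "Deadline for data analysis: 31-03-2019".

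The primary endpoint in section 2.3, overall survival, is "defined as the time interval between the date of discovery of adrenal incidentaloma and the date of death from any cause". Event-free survival starts from the same date.

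On analysis, section 2.4 plans Kaplan-Meier curves, from which risks are to be read. For the models it states that "Cox regression will be used for time-to-event analysis, and hazard ratios (HRs) computed with accompanying 95% confidence intervals (95% CI". The groups to be compared are defined by cortisol alone: "Analysis will be stratified according to post-dexamethasone cortisol levels with three pre-specified cutoffs". The only other planned split is Cohort A against Cohort B, which depends on completeness of data. No section uses year of diagnosis, or the 2000 versus 1996 window, as a covariate, stratum or sensitivity analysis. Date of diagnosis is nevertheless among the minimum annotations in section 2.5, and Cohort B patients must have it too.

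**The concern.** The change adds four years of diagnoses, 19 to 23 years old when retrieved, to a retrospective comparison with no stated adjustment. Two things could differ between those patients and later ones: the mix of cortisol bands (for example, if dexamethasone testing was more selective in the 1990s) and the underlying rate of death or cardiovascular events. If both differ, the hazard ratio between bands partly measures era. Overall survival is the primary endpoint, and the hazard ratios by band are the study's main product.

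The curves are affected as well. The added patients make up a growing share of the risk set as follow-up lengthens, so risks quoted at 15 years or later lean on them heavily. Longer follow-up was the stated purpose of the change, so readers will look at those late risks.

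**Working it through.** The plan states no figure to reproduce, so the check is calendar arithmetic followed by two illustrations.

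**Maximum follow-up.** Inputs: window starts 1-1-2000 and 1-1-1996 (section 2.5); end of data 30 November 2018 (section 2.8). Formula: days between the dates / 365.25.
- Diagnosed 1-1-2000: 18.91 years. This becomes 18.75 if data end on 1 October 2018 and 19.24 if they run to 31 March 2019.
- Diagnosed 1-1-1996: 22.91 years.
- From the change (1 to 31 October 2018) to 30 November 2018: 60 to 30 days.

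**Share supplied by 1996-1999, uniform accrual.** Assumptions: diagnoses spread evenly from 1-1-1996 to 30-11-2015 (the last date allowing 36 months), no deaths or losses. Let T = 22.913 years; the accrual window is T − 3 = 19.913 years, of which the first 4 are the added years.
- Patients: 4 / 19.913 = 20%.
- Person-time: (22.913² − 18.913²) / (22.913² − 3²) = 167.3 / 516.0 = 32%.
- At risk at t years: 4 / (22.913 − t), giving 31% at 10 years, 51% at 15 and 81% at 18.
- Person-time beyond 18.9 years, all from 1996-1999: 4² / 516.0 = 3.1%.

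**Same, with accrual growing 10% per year.** Weight exp(0.10x) at x years after 1-1-1996.
- Patients: (e^0.4 − 1) / (e^1.9913 − 1) = 0.492 / 6.325 = 8%.
- At risk at t years: (e^0.4 − 1) / (e^(0.10(22.913 − t)) − 1), giving 19% at 10 years, 41% at 15 and 78% at 18.
- Person-time, by numerical integration of weight × follow-up: 16% (17% if growth is compounded annually).
- Person-time beyond 18.9 years: 1.5%.

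**Effect on a hazard ratio.** Assumptions, none from the documents: the true band hazard ratio is 1.0; early-era mortality is h times later mortality; 30% of the high band and 10% of the low band are early-era. Apparent ratio ≈ (0.7 + 0.3h) / (0.9 + 0.1h).
- h = 1.2: 1.06 / 1.02 = 1.04.
- h = 1.5: 1.15 / 1.05 = 1.10.
- Imbalance reversed: 1.02 / 1.06 = 0.96 and 1.05 / 1.15 = 0.91.

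The 30% and 10% split suits the uniform scenario (20% early-era overall). It fits poorly with the growth scenario, where an overall 8% would require the middle band to be below 8%.

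**The case against.** The earliest entrants supply the tail of any cohort with staggered entry. Had the window stayed at 2000, the tail would have come from the first years after 2000. Section 2.5 states the reason for the change openly. Time beyond 18.9 years is so small a part of the total that a Cox estimate draws little from it. The hazard-ratio bias needs an era difference in risk and a threefold imbalance between bands, and the documents show neither. Section 2.4 is a short outline that names no adjustment covariates, not even age or sex, so diagnosis period is one instance of a wider gap, and pooling of eras is inferred from silence. All of this stands, and it limits the point to a precaution.

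A reader might infer four stronger things, which the documents do not support.
- That the late part of the curves reflects outdated care. Time beyond 18.9 years falls at about calendar 2014.9 to 2018.9; only the diagnosis is old.
- That centres had already assembled cases under the 2000 rule, so that the added years come from a subset of centres. Nothing says so; centres could still join until 31-10-2018, and the authorship rule in section 3 rewards larger contributions. Loss of old records is also likely to be graded, with no break at 1-1-2000.
- That results had been seen before the window was widened. The documents do not suggest it.
- That curves should stop at 18.9 years. The risk set is already about half early-era at 15 years and 81% at 18 under uniform accrual, so such a cut would not remove the dependence.

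The objection does not remove the case for using diagnosis period. The comparison is observational, a substantial share of person-time may come from the added years, and the variable is already collected.

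**Conclusion.** The point holds as a recommended improvement; no error is demonstrated. The dates and the absence of any diagnosis-period term are facts of the plan. Confounding by era is conditional: it requires both band mix and risk to differ by era, and its direction is unknown. At the illustrated sizes a null hazard ratio moves by no more than about 10% either way. That is modest, but it matters if the true differences between bands are small. The 20% and 32% (or 8% and 16%) shares rest on assumed accrual patterns without deaths or losses. The 18.9-year figure rests on follow-up ending at the planned data deadline, and plausible end dates move it only between 18.7 and 19.2 years.

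**What to change.** In section 2.4:
1. Stratify the Cox baseline hazard by period of diagnosis, or adjust for it, with cut-points fixed in advance and one of them at 1-1-2000. Cortisol band stays the compared factor. The text should keep this use of stratification distinct from its present use for the cortisol bands.
2. Repeat overall survival and event-free survival restricted to diagnoses from 1-1-2000, as a sensitivity analysis.
3. Print numbers at risk under every Kaplan-Meier curve, with no fixed 18.9-year cut, so that the reader can see where late estimates become thin.

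In section 2.8, replace 31-11-2018 with a real date.

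No new data are needed. The cost is a few sentences, a few extra model runs (possibly in both Cohorts A and B) and a slight loss of precision from stratifying. The restricted analysis will be less precise than the main one because it drops the added years. If the two agree, the wider window is supported; if they differ, the report should say so.

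### Patients who qualify only by an unchanged follow-up scan at or after 12 months have survival counted from discovery, so the time before that scan cannot contain a death

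*Combined protocol and SAP*

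**What the plan says.** Three parts of the combined protocol and SAP bear on this.

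- **Eligibility (section 2.5).** The mass must look typical of an adenoma on CT, chemical-shift MRI or FDG-PET. A fallback is then allowed: "In the absence of appropriate imaging study, results of 12-month follow-up showing unchanged mass characteristics can be considered as surrogate criterion". The list of minimum annotations words the fallback differently: "imaging during follow-up > 12 months after initial imaging demonstrating unchanged tumor size". The list asks for the date of diagnosis, but not for the date of the scan that made the patient eligible. A separate criterion asks every patient for at least 36 months of follow-up from first diagnosis, without saying whether people who die earlier are kept.
- **Time origin (section 2.3).** OS, the primary endpoint, is "defined as the time interval between the date of discovery of adrenal incidentaloma and the date of death from any cause". ES uses the same origin: "defined as the time interval between the date of discovery of adrenal incidentaloma and the date of occurrence of a" major or minor CV event. CV mortality has no separate clock; I assume it follows OS.
- **Analysis (section 2.4).** "Kaplan-Meier analysis will be used to construct survival curves and compute risks", Cox regression gives the hazard ratios by cortisol band, and "CV event rates will be expressed as the number of events per 1000 person-years". Delayed entry, left truncation and a landmark are not mentioned.

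**The concern.** For patients on the fallback route, eligibility is settled by something that happens a year or more after time zero. Someone with no appropriate imaging study who dies at month 8 can never supply the unchanged scan and is never in the data. Someone who lives to be scanned enters with all the time since discovery credited as time at risk. That interval holds person-time but, by construction, no deaths. Because the annotation list sets no upper limit on when the scan may be taken, the credited interval may be much longer than a year.

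The study sets out to describe mortality and to estimate hazard ratios by post-dexamethasone cortisol. Guaranteed survival lowers the absolute risks. If one cortisol band relies on the fallback more than another, it also distorts the comparison between bands. Without the scan date, the problem can be neither corrected nor measured at the analysis stage.

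**Working it through.** The plan gives no total sample size, event count or mortality figure, so there is nothing of its own to reproduce. The logic comes from the text; the size below is illustrative.

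**Step 1: closed form, scan at exactly 12 months, deaths before month 36 admitted.** Assumed inputs, none in the documents: hazard h of 0.01-0.03 per year, follow-up T of 5-10 years, share s of included patients on the fallback route of 10-50%. L = 1 year.

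- Other patients: deaths D0 = 1 − exp(−hT); person-years P0 = D0/h.
- Fallback patients (alive at L): deaths D1 = 1 − exp(−h(T−L)); person-years P1 = L + D1/h.
- Rate with the clock at discovery = [(1−s)D0 + sD1] / [(1−s)P0 + sP1].

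Largest effect in the range (h = 0.03, T = 5, s = 0.5): D0 = 0.1393, P0 = 4.643, D1 = 0.1131, P1 = 4.769. Rate = (0.0697 + 0.0565)/(2.322 + 2.385) = 0.0268, or 26.8 per 1000 person-years against a true 30: 11% low. Within the fallback subgroup alone it is 0.1131/4.769 = 0.0237, 21% low.

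Smallest effect (h = 0.01, T = 10, s = 0.1): D0 = 0.0952, P0 = 9.516, D1 = 0.0861, P1 = 9.607. Rate = 0.0943/9.525 = 0.0099 against 0.0100: 1% low.

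Counting fallback patients from L instead gives D1/(P1 − L) = h, the true rate.

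**Step 2: direction of the ratio.** Same formula, T = 5, reference hazard 0.015, true ratio 1.50:

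| Share, reference band | Share, high band | Ratio obtained |
|---|---|---|
| 30% | 30% | 1.498 |
| 10% | 50% | 0.02015/0.01469 = 1.37 |
| 50% | 10% | 0.02203/0.01345 = 1.64 |

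Equal shares leave the ratio essentially intact. Unequal shares move it either way.

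**Step 3: simulation with a variable scan date and both readings of the 36-month rule.** 2,000,000 patients per band, no true difference, 3% deaths per year, administrative follow-up uniform from 3 to 22.9 years (22.9 is roughly 1-1-1996 to the end-November 2018 data deadline). The scan falls at 12 months plus an exponential delay, and a fallback patient is kept only if the scan comes before death or end of follow-up. The person-years rate ratio stands in for the hazard ratio.

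| Shares, reference vs high | Mean extra delay | Deaths before month 36 admitted |
|---|---|---|
| 10% vs 30% | none | 0.98 |
| 10% vs 30% | 0.5 to 3 years | 0.97 to 0.94 |
| 20% vs 50% | none | 0.97 |
| 20% vs 50% | 0.5 to 3 years | 0.96 to 0.91 |
| 30% vs 30% | 0.5 to 3 years | 1.00 (rates 0.0288 to 0.0275 against 0.030: 4-8% low) |

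If survival to month 36 is required of everyone, the ratios are 0.97-1.00. Swapping the shares between bands inverts a null ratio: 1/0.98 = 1.02 to 1/0.91 = 1.10 in the admitted case.

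**Step 4: does delayed entry repair it?**

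- Deaths before month 36 admitted, entry at the scan: 0.0300 in both bands, ratio 1.00.
- Survival to month 36 required, entry at the scan for fallback patients only: rates of 0.022-0.024 against 0.030, and a spurious person-years ratio of 1.02-1.07 (the Cox ratio stays near 1.00). Guaranteed survival has been removed from one subgroup and left in the rest.
- Survival to month 36 required, everyone entered at month 36 or at the scan if later: rates 0.030, ratio 1.00.

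**The case against.** The strongest reply is that the 36-month criterion is the larger problem and contains most of this one. If it requires survival to month 36, every patient has three guaranteed years, and a scan before month 36 adds nothing. Under the Step 1 hazards and follow-up, that rule alone brings the rate down to 39-69% of its true value. This stands, and it is why the ratio is only 0.97-1.00 on that reading. It does not dispose of the point: admitting early deaths cures the 36-month problem but not this one, and a scan after month 36 extends the guaranteed interval on either reading.

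The lowest ratios also need long delays: 0.91 assumes half the high band on this route and a mean scan time of four years. With the scan at exactly 12 months, the ratio is 0.97-0.98. That stands too.

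A reader might infer more than the documents support, in three ways:

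- **That everyone with poor first imaging is affected.** Section 2.5 does not confine the accepted studies to the first scan. A patient characterised soon afterwards by CT, MRI or PET qualifies without the fallback. Simply not being re-scanned is non-inclusion, not in itself immortal time.
- **That the hazard ratio is pulled down.** That needs the fallback to be commoner in the higher bands. Nothing in the documents says so, and the opposite imbalance pushes the ratio up.
- **That ES is affected as OS is.** A non-fatal CV event before the scan does not bar a patient from inclusion. Only fatal events are excluded from the interval.

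**Conclusion.** The point holds for a defined subgroup: patients who never had an appropriate characterising study and qualify by the follow-up scan alone. For them the time from discovery to the scan is immortal for death in OS, and in CV mortality if it shares the OS clock. In ES it is immortal for fatal events only. Their absolute mortality is understated, and the cohort's with it: by about 1-11% over the Step 1 range, and by 4-8% at a 30% share with the variable delays of Step 3, both with deaths before month 36 admitted.

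The hazard ratio is biased only through unequal use of the route. With 10-20% in the reference band against 30-50% in the high band, a null ratio becomes about 0.91-0.98 if deaths before month 36 are admitted and 0.97-1.00 if survival to month 36 is required. Reversed shares reverse the direction. Shares, hazards and delays are all assumptions. The bias is modest but cheap to remove, so it should be corrected. The two wordings of the criterion (interval, and size against characteristics) are a smaller matter, but could lead centres to admit different patients.

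**What to change.** 1. Ask centres for the date of the qualifying scan for every patient who meets the adenoma criterion only through follow-up imaging.
2. State one handling of the 36-month rule and tie entry to it. If deaths before month 36 are admitted, fallback patients enter the risk set at the scan and all others at discovery. If survival to month 36 is required, every patient enters at month 36, or at the scan if later. Apply this to OS and CV mortality in Kaplan-Meier, Cox and person-years. Entry at the scan without settling the 36-month rule is not enough (Step 4).
3. For ES, use the same entry times, report how many first CV events before entry are set aside, and add a sensitivity analysis excluding patients on this route.
4. Report the share on this route by cortisol band, so that readers can judge the direction of any remaining bias.
5. Reconcile the two statements of the criterion in section 2.5 so that both give the same interval and the same requirement.

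The cost is one date field, a start-time variable in the analysis file and one table. The downside is that early person-time and some early non-fatal CV events are not used.
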